### **7.3 Tertiary endpoints**

We will also tabulate the number of genotype results returned, the average genotype test completion time, the genotype assay failure rate, the number of and reason for screening failure, time from test order to result in medical record, and patient/prescriber attitudes towards PGx test results.

### **7.4 Post-hoc analyses**

Genotyped will be determined in the control group at the end of the trial. We will combine the groups and evaluate outcomes by CYP2C19 genotype and antiplatelet drugs prescribed at discharge.

Participants will be grouped into the following categories: 1) Carriers of normal function alleles receiving any antiplatelet drug, 2) LOF carriers receiving clopidogrel, or 3) LOF carriers receiving prasugrel or ticagrelor. Time to MACE, major bleeding and a composite safety/efficacy endpoint consisting of MACE, major bleeding and non-cardiac mortality will be determined in the three groups. Cox proportional hazards models will be used to assess the effects of having an LOF allele and receiving clopidogrel therapy, having an LOF allele and receiving alternative therapy, and not having an LOF allele on the occurrence of first MACE, first major bleed, and first composite outcome. The Cox model will be controlled for age at entry to the study, the date of catheterization, gender, race, hospital site, and history of ACS, smoking, hypertension, diabetes, and myocardial infarction.

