### **4.0 STUDY DESIGN**

[figure not shown]
This is a randomized, prospective, pragmatic open label pilot study (Figure 1). Patients undergoing PCI with stent implantation, who require anti-platelet therapy, will be randomized to: Arm 1) genotype guided dosing of antiplatelet therapy or Arm 2) usual care. Randomization will be stratified by the occurrence of acute coronary syndrome (ACS).

In Arm 1, a buccal swab will be obtained from subjects immediately following PCI/stent, to determine *CYP2C19* genotype with the SpartanRx system. This arm provides pharmacogenetic information to help guide decision making: initiation of therapy with prasugrel or ticagrelor will be recommended for participants found to be slow metabolizers [1 or 2 loss-of-function (LOF) mutations (\*2 or \*3) in *CYP2C19*]; initiation of therapy with clopidogrel will be recommended for participants found to be normal metabolizers (*CYP2C19* \*1/\*1). See Table 1 and Appendix A. Antiplatelet choice will ultimately be decided by the treating physician taking into account all clinical factors.

In Arm 2, the choice of antiplatelet therapy will be decided by the treating physician as per usual care. DNA will be collected by –saliva sample and *CYP2C19* genotype will be determined at the completion of the study.

Subjects in both groups will complete baseline health related quality of life questionnaire (HrQoL). Subjects will be contacted every three months for clinical information, medical service utilization and HrQoL assessments. No specific recommendations will be made regarding use of vorapaxar, a recently approved anti-platelet agent for which guideline-based recommendations regarding genotyping are not available.

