### **7.5 Sample size for Primary Outcome**

The sample size calculation is based on two factors: 1) the rate of pre-study prasugrel/ticagrelor antiplatelet therapy prescribing (20%) and 2) anticipated increase in alternative antiplatelet prescribing based on the frequency CYP2C19 LOF variants (~30-35%). We estimate a 15% difference in the use of prasugrel/ticagrelor prescriptions in the two groups (35% in the genotype group and 20% in the control group). A sample size of 138 per group (a total of 276) would provide 80% power at an alpha level of 0.05 to detect this difference. We will increase our sample size to ~250 per group to allow for subgroup comparisons (e.g. ACS vs. stable coronary disease).

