
 
Do not use prasugrel in patients with active bleeding or a history of transient ischemic attack or stroke.
 
Individual risks/benefits of prasugrel must be carefully considered in patients over age 75.
 
Do not start prasugrel in patients likely to undergo urgent coronary bypass graft surgery (CABG).
 
Consider prasugrel 5 mg per day for patients <60 kg.
 
	
 
Do not use ticagrelor in patients with active bleeding or a history of transient ischemic attack or stroke.
 
Do not start ticagrelor in patients likely to undergo urgent coronary bypass graft surgery (CABG).
 
Do not use maintenance aspirin dose above 100 mg in combination with ticagrelor.
 
Avoid with strong CYP3A inhibitors or inducers.
 

1. Scott, S.A. et al. Clinical Pharmacogenetics Implementation Consortium Guidelines for CYP2C19 Genotype and Clopidogrel Therapy: 2013 Update. *Clin Pharmacol Ther* **94**, 317-23 (2013).

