Additional analyses	29	Post-hoc analyses Genotype was determined in the control group at the end of the trial. We combined the groups and evaluated outcomes by CYP2C19 genotype and antiplatelet drugs prescribed at discharge. Participants were grouped into the following categories: 1) Carriers of normal function alleles receiving any antiplatelet drug, 2) LOF carriers receiving clopidogrel, or 3) LOF carriers receiving prasugrel or ticagrelor. Time to MACE, major bleeding and a composite safety/efficacy endpoint consisting of MACE, major bleeding and non-cardiac mortality was determined in the three groups. Cox proportional hazards models were used to assess the effects of having an LOF allele and receiving clopidogrel therapy, having an LOF allele and receiving alternative therapy, and not having an LOF allele on the occurrence of first MACE, first major bleed, and first composite outcome. The Cox model was controlled for age at entry to the study, the date of catheterization, gender, race, hospital site, and history of ACS, smoking, hypertension, diabetes, and myocardial infarction.
Harms	30	No harms as a result of the genotyping intervention were reported.
Statistical software	31	Stata's V13.1 (College Lake, TX)
References	32	
1.Mega, J.L. et al. Reduced-function CYP2C19 genotype and risk of adverse clinical outcomes among patients treated with clopidogrel predominantly for PCI: a meta-analysis. JAMA 304, 1821-30 (2010).
 
2.Scott, S.A. et al. Clinical Pharmacogenetics Implementation Consortium Guidelines for CYP2C19 Genotype and Clopidogrel Therapy: 2013 Update. Clin Pharmacol Ther 94, 317-23 (2013).
 
 
4.Mehran, R. et al. Standardized Bleeding Definitions for Cardiovascular Clinical Trials: A Consensus Report From the Bleeding Academic Research Consortium. Circulation 123, 2736-47 (2011).

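### Genotype from both arms is used only in a pooled analysis by physician-chosen drug; the comparison of carriers by randomised arm, available from data already collected, is not planned.

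*Protocol*

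**What the plan says.** Protocol 7.4: "We will combine the groups and evaluate outcomes by CYP2C19 genotype and antiplatelet drugs prescribed at discharge". SAP item 29, in the past tense: "We combined the groups and evaluated outcomes by CYP2C19 genotype and antiplatelet drugs prescribed at discharge". Both documents form three groups: participants named by carriage of normal-function alleles, on any drug; LOF carriers on clopidogrel; and LOF carriers on prasugrel or ticagrelor. Cox models for first MACE, first major bleed and a composite adjust for ten covariates: age, catheterization date, gender, race, site, ACS, smoking, hypertension, diabetes and MI. Randomised arm is not among them.

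On who picks the drug, Protocol 4.0 says of Arm 1: "Antiplatelet choice will ultimately be decided by the treating physician taking into account all clinical factors". In Arm 2 the physician decides as in usual care.

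The planned comparisons by randomised arm are prescribing at discharge (Protocol 7.1, SAP 27a), MACE and major bleeding in all participants (Protocol 7.2, SAP 27a), and an ACS × arm interaction for MACE (Protocol 7.2, SAP 27f). Adherence to the genotype recommendation is defined in Arm 1 only (SAP 19a-19b).

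Arm 1 is genotyped on the rapid device at PCI. Arm 2 is genotyped from saliva at study end (Protocol 6.2). Saliva is taken from everyone (Protocol 6.7).

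**The concern.** Two carriers in the pooled analysis can be on different drugs because they were randomised differently or because a physician judged them differently. The second route matters most in Arm 1, where a carrier left on clopidogrel is one whose physician did not follow the recommendation. The trial collects reasons for non-adherence, but the Cox model does not use them. If those reasons also predict events, the estimated drug effect absorbs them.

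A germline genotype is not altered by randomisation, so carriers in Arm 1 and carriers in Arm 2 are comparable by design. That contrast asks directly whether reporting an LOF result changed prescribing and outcome. Neither document includes it, for prescribing, MACE or bleeding.

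The planned full-cohort comparison does not fill the gap. Carriers are steered towards prasugrel or ticagrelor and non-carriers towards clopidogrel, so the overall difference nets two opposite movements. A small net difference could hide a full response by physicians.

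**Working it through.** **The plan's own figure.** Protocol 7.5: "A sample size of 138 per group (a total of 276) would provide 80% power at an alpha level of 0.05", for "35% in the genotype group and 20% in the control group". Pooled two-proportion formula, two-sided, mean rate 0.275:

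n = [1.96 × √(2 × 0.275 × 0.725) + 0.842 × √(0.35 × 0.65 + 0.20 × 0.80)]² / 0.15² = 137.9, so 138 per group. This reproduces. At 250 per group power is 96.6%.

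**Carriers available.** Protocol 7.5 gives an LOF frequency of about 30-35% and a target of about 250 per group. 500 × 0.30 = 150 and 500 × 0.35 = 175, or about 75-87 per arm.

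**Netting in the full cohort.** Assume full adherence in Arm 1 and 20% use in Arm 2 regardless of genotype. Carriers move by 100 − 20 = +80 points and non-carriers by 0 − 20 = −20. The net is 0.30 × 80 − 0.70 × 20 = +10 points, or 0.35 × 80 − 0.65 × 20 = +15 points.

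**Size of possible confounding (illustration; every input assumed).** No true drug effect; 30% of carriers have an unmeasured risk factor; equal arms; overall alternative use 70% in Arm 1 and 20% in Arm 2; less use in high-risk carriers.

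| Alternative use, high-risk vs other carriers | High-risk share on clopidogrel / alternative | Ratio if risk doubles | Ratio if risk triples |
|---|---|---|---|
| Arm 1: 50% vs 78.6%; Arm 2: 10% vs 24.3% | 38.2% / 20.0% | 1.382/1.200 = 1.15 | 1.764/1.400 = 1.26 |
| Arm 1: 40% vs 83%; Arm 2: 5% vs 26.4% | 42.3% / 15.0% | 1.423/1.150 = 1.24 | 1.846/1.300 = 1.42 |

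These are crude ratios, before adjustment. By randomised arm, the high-risk share is 30% on both sides and the ratio is 1.0.

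**By-arm contrast in carriers, prescribing.** Same formula, 20% use in Arm 2 carriers, 75-87 per arm: power is 77-83% if Arm 1 use is 40%, 98-99% at 50%, and above 99% at 60%.

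**By-arm contrast in carriers, MACE.** The documents give no event rate.

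- Precision at an assumed 10%: 15 to 17.5 events. Standard error of log HR ≈ 2/√events = 0.516 to 0.478. The 95% interval is a factor exp(1.96 × SE) = 2.75 to 2.55 either way, about 2.6-2.8.
- Power, taking a clopidogrel-versus-alternative HR of 1.55 (borrowed from the carrier-versus-noncarrier figure in Protocol 2.0) and events at 5-15%: Arm 2 mean hazard 0.8 × 1.55 + 0.2 = 1.44. With 100%, 70% or 50% alternative use in Arm 1 carriers, the Arm 1 mean is 1.00, 1.165 or 1.275, so the by-arm HR is 1.44, 1.24 or 1.13. With 8-26 events, power is about 4-15%.
- The planned drug-received contrast has about 8-20% power in the same carriers under the same assumptions.

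**The case against.** Much can be said for the plan, and most of it stands.

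- **The randomised evidence is not thrown away.** A reader might infer that it is. The primary endpoint is a randomised prescribing comparison, and MACE and major bleeding are compared by arm in everyone. What is missing is the split by genotype.
- **The pooled analysis is labelled post-hoc, is adjusted, and supports no primary claim.** It asks about genotype-drug combinations, which is a different question. The by-arm contrast supplements it and does not replace it.
- **The handout does not supply a list of omitted confounders.** A reader might point to body weight and interacting drugs. The weight item is a dose note for prasugrel. The caution "Avoid with strong CYP3A inhibitors or inducers" is listed for ticagrelor only, which leaves prasugrel. As written, neither puts a carrier in the clopidogrel group. Nor does the model lack every bleeding-related factor: age is included, and active bleeding, prior stroke or TIA, pending surgery and long-term anticoagulation are exclusions. Residual confounding is possible, not shown.
- **A larger false ratio is easy to compute.** If 80% of high-risk and 30% of other carriers stay on clopidogrel, ignoring arm, the ratios are 1.38 and 1.70. That scenario has 0.3 × 0.2 + 0.7 × 0.7 = 55% on the alternative, which with 20% in Arm 2 needs 90% in Arm 1. It also treats all variation in drug as selection.
- **The by-arm contrast is not automatically free of bias.** Carrier status comes from different assays by arm, inconclusive Arm 1 results are anticipated, and the modified intention-to-treat set removes ineligible participants in an open-label trial.

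The objection does not answer the central gap. The carrier contrast by arm is absent, and nothing else in the plan shows how carriers responded relative to a control.

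**Conclusion.** The point holds as a worthwhile, low-cost improvement. The only planned use of genotype from both arms rests on physician choice, and the protected comparison that the design offers is left out. It would be informative for prescribing under the assumed 20% use in Arm 2 carriers. It could not settle MACE at this size; however, the drug-received contrast is also weak there, so it gains little precision for the protection it gives up.

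The confounding ratios are an illustration of what is possible under assumed inputs and before adjustment. They do not estimate the bias in this trial, and the documents do not support saying that the planned hazard ratio is wrong.

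**What to change.** In Protocol 7.4 and SAP item 29:

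1. Add a comparison of Arm 1 with Arm 2 within LOF carriers and within non-carriers, for discharge prasugrel/ticagrelor use, MACE, major bleeding and the composite, with 95% confidence intervals and a genotype × arm interaction. The protocol enlarged the trial with this kind of use in mind: "We will increase our sample size to ~250 per group to allow for subgroup comparisons".
2. Define carrier status in the same way in both arms, ideally from the saliva assay if consent covers it for Arm 1, and handle inconclusive results alike.
3. State that the three-group Cox model is an observational comparison.
4. Reword its first group as no LOF allele. \*1/\*2 and \*1/\*3 patients also carry a normal-function allele, so the present label overlaps the other two groups.

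Cost: extra exploratory analyses, with no multiplicity correction (SAP item 17), on data largely in hand; assaying Arm 1 saliva would be additional work. The MACE result must be presented as an estimate with a wide interval, not as a test.

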### **7.5 Sample size for Primary Outcome**

The sample size calculation is based on two factors: 1) the rate of pre-study prasugrel/ticagrelor antiplatelet therapy prescribing (20%) and 2) anticipated increase in alternative antiplatelet prescribing based on the frequency CYP2C19 LOF variants (~30-35%). We estimate a 15% difference in the use of prasugrel/ticagrelor prescriptions in the two groups (35% in the genotype group and 20% in the control group). A sample size of 138 per group (a total of 276) would provide 80% power at an alpha level of 0.05 to detect this difference. We will increase our sample size to ~250 per group to allow for subgroup comparisons (e.g. ACS vs. stable coronary disease).

### **7.6 Sample Size for Economic Evaluation**

While there is little published guidance on sample size determination for pilot studies, we present confidence intervals that will result for expected population means and standard deviations and a sample size of 350 per treatment arm (see Table 2). Knowing the expected mean and standard deviation of hospital cost will be important when designing the more definitive study of the cost-effectiveness of genotype guided dosing of anti-platelet therapy.

Given that hospital cost distributions typically have long heavy right tails, we assume that these costs are distributed log normally. There are limited data on the expected cost and expected standard deviation for a year of hospital costs after initiation of antiplatelet therapy. We have derived our “baseline” assumptions (mean = \$7800; SD = \$9355) from Nikolic et al., a European study that may or may not be representative of costs in the U.S.

Simulation indicates that for a sample size of 350 per group (total N = 700) if the population mean is 7800 and the average standard deviation for repeated draws of participants is 9355, then if we repeated the pilot study 1000 times, in 95% of them the observed mean would range between 6851 and 8775 and the observed standard deviation would range between 6875 and 13138 (see row 2 of Table 2). Rows 1 and 3 of the table indicate that if we are incorrect that the average standard deviation from repeated draws is 9355, the expected standard deviations in 95% of repeated experiments would range between 4942 and 7499 if average standard deviation for repeated draws were 6000. It would range between 7853 and 19423 if the average standard deviation were 12,000.

Rows 4-6 report sensitivity analyses for cases in which we assume the population mean is 10,000; rows 7-9 report these analyses for cases in which we assume the population mean is 15,000. In the

most extreme case (population mean 15,000, average SD from repeated draws of 18000), in 95% of repeated experiments the mean would fall in the range between 13,345 and 17,044 and the standard deviation would fall in the range between 13,240 and 25,658.

Substitution of the more realistic assumption of log normality for the less realistic assumption of normality increased the magnitude of the average range of the standard deviation by more than 300%. Assuming log normality, but substitution of a sample size of 175 per group (total N=350) for the proposed 350 per group would lead to an average increase in the magnitude of the ranges of 32%.

**Table 2. Expected 95% Confidence Intervals for Sample Means and Sample Standard Deviations for Hospital Cost in Dollars Given Varying Population Means and Standard Deviations, N = 350 per Treatment Group\***

Population Mean	95% Confidence Interval for Mean	Population Standard Deviation	95% Confidence Interval for Standard Deviation
1. 7800	7248 to 8471	6000	4942 to 7499
2. 7800	6851 to 8775	9355	6875 to 13138
3. 7800	6633 to 9125	12,000	7853 to 19,423
4. 10,000	9300 to 10,774	7000	5771 to 8478
5. 10,000	9021 to 11,164	10,000	7732 to 13,529
6. 10,000	8715 to 11,393	13,000	9252 to 18,413
7. 15,000	13,771 to 16,249	12,000	9641 to 5203
8. 15,000	13,510 to 16,778	15,000	11,550 to 19,889
9. 15,000	13,345 to 17,044	18,000	13,240 to 25,638

\* Costs assumed to be log normally distributed. Estimates derived from simulation.

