### Section 3: Study Methods

Section/Item	Index	Description
Trial Design	9	This was a prospective, pragmatic, randomized, controlled clinical pharmacogenetic implementation trial. Patients undergoing PCI with stent implantation requiring anti-platelet therapy were randomized 1:1 to either rapid genotyping of CYP2C19 with reporting of results to the interventional cardiologist or no genotyping (usual care).
Randomization	10	We used Stata's V13.1 (College Lake, TX) random number generator to draw random numbers that were used to randomize participants to the genotyping and usual care groups. Randomization was stratified by hospital site and by the presence or absence of ACS. Acute coronary syndrome was defined as unstable angina, non-ST elevation myocardial infarction, or ST-elevation myocardial infarction. The designation of ACS vs. stable angina was made by the treating interventional cardiologist. Within each of the four groups, randomization was balanced so that after every 10 patients, 5 were randomized to the genotyped group and 5 to usual care.
Sample size	11	The sample size calculation was based on two factors: 1) the rate of pre-study prasugrel/ticagrelor use (20%) and 2) anticipated increase in prasugrel/ticagrelor prescribing based on the frequency CYP2C19 LOF variants (~30-35%). We estimated a 15% difference in the use of prasugrel/ticagrelor in the two groups (35% in the genotyped group and 20% in the control group). A sample size of 138 per group (a total of 276) would provide 80% power at an alpha level of 0.05 to detect this difference. We increased our sample size to ~250 per group to allow for subgroup comparisons (e.g. ACS vs. stable coronary disease).
Framework	12	Genotyping will increase the prescribing of prasugrel or ticagrelor from the baseline rate of 20%.
Statistical interim analyses and stopping guidance	13	No interim analyses planned.
Timing of final analysis	14	Participants were followed until May 31, 2017 for prospective clinical endpoints assessment with the intention of a 12 month follow-up time for each participant. All analyses were performed collectively after May 31, 2017.

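### Protocol 7.6 and Table 2 state hospital-cost precision for 350 per arm (700 in total), but the trial plans about 250 per group (500-600 in total), so the stated ranges are moderately too narrow

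*Protocol*

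**What the plan says.** Protocol 7.6 is the only sample-size justification for the economic pilot aim. It assumes lognormal hospital costs and reports the ranges expected to hold the observed mean and SD in 95% of repeated pilots. The simulation result opens with "Simulation indicates that for a sample size of 350 per group (total N = 700". Table 2 carries the label "N = 350 per Treatment Group". The section treats 350 per group as the plan and half of it as the alternative: "substitution of a sample size of 175 per group (total N=350) for the proposed 350 per group would lead to an average increase" in the width of the ranges, put at 32%.

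The other statements of trial size are smaller:

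- Protocol 7.5, after deriving 138 per group for the primary outcome: "We will increase our sample size to ~250 per group to allow for subgroup comparisons".
- SAP item 11, in the past tense: "We increased our sample size to ~250 per group to allow for subgroup comparisons".
- Protocol Synopsis, number of subjects: 500-600.
- SAP item 9 on allocation: participants "were randomized 1:1 to either rapid genotyping" or usual care. With equal allocation, 500-600 in total means 250-300 per arm.

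No passage explains the difference or plans separate enrolment for the economic aim.

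**The concern.** Even the top of the Synopsis range, 600, is 100 short of the 700 on which Section 7.6 rests. Estimating the mean and variance of cost is a stated objective, and Section 7.6 says these estimates matter for designing the definitive study. Precision is the whole content of that section, so using the wrong size undermines the one thing it sets out to show. The error is also in the favourable direction: the pilot looks more precise than it will be. The reader cannot recover the right figures from the plan, because the only other size discussed, 175 per group, lies below the planned range.

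**Working it through.** **Inputs.** Cost is lognormal, with nine pairs of population mean and SD (Protocol 7.6, Table 2). The plan's simulation used 1,000 replicates. Sizes per arm: 350 (Section 7.6), 250 (Section 7.5, SAP item 11), 300 (600 / 2, Synopsis) and 175 (the alternative in Section 7.6).

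**Method.** For each row, σ² = ln(1 + (SD/mean)²) and μ = ln(mean) − σ²/2. For row 2 (mean 7,800, SD 9,355), σ² = ln(1 + 1.1994²) = 0.891 and μ = 8.962 − 0.446 = 8.516. Draw samples of size n and take the 2.5th and 97.5th percentiles of the sample mean and the sample SD. The figures below use 100,000 draws per row unless stated.

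**1. The plan's figures at 350 per arm.** Row 2 gives a mean range of 6,888-8,845 (plan 6,851-8,775) and an SD range of 6,815-13,282 (plan 6,875-13,138). In the other rows the limits agree within about 3%, which 1,000 replicates can explain. The exception is the row 7 upper SD limit (step 6).

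**2. Is 350 a mislabelled total?** No. At 175 per arm, row 2 would be 6,536-9,314 for the mean and 6,130-14,562 for the SD (20,000 draws). The printed row does not match these.

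**3. The plan's 32%.** Going from 350 to 175 per arm, the SD ranges widen 31% on average, which agrees with the plan. The mean ranges widen 41%, and √2 = 1.41.

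**4. The planned sizes, row 2.** Every size uses the same simulation, so the comparison is like for like.

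| Per arm | Mean range | Width | SD range | Width |
|---|---|---|---|---|
| 350 | 6,888-8,845 | 1,957 | 6,815-13,282 | 6,467 |
| 300 | 6,812-8,930 | 2,118 | 6,672-13,561 | 6,889 |
| 250 | 6,728-9,056 | 2,328 | 6,498-13,970 | 7,472 |

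Width ratios for row 2 at 250 per arm: 2,328 / 1,957 = 1.19 (mean) and 7,472 / 6,467 = 1.16 (SD). At 300 per arm: 2,118 / 1,957 = 1.08 and 6,889 / 6,467 = 1.07.

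Averaged over nine rows, relative to 350 per arm:

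- 250 per arm: mean ranges 18% wider (17-19% by row), SD ranges 14% wider (11-17%).
- 300 per arm: about 8% and 7% wider.

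For the means, √(350/250) = 1.183 and √(350/300) = 1.080 agree. A repeat with 20,000 draws per row gives 18% and 15% at 250, and 7% and 6% at 300.

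**5. All rows: the plan at 350 against simulation at 250 per arm.**

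| Row | Mean, plan (350) | Mean at 250 | SD, plan (350) | SD at 250 |
|---|---|---|---|---|
| 1 | 7,248-8,471 | 7,083-8,574 | 4,942-7,499 | 4,753-7,680 |
| 2 | 6,851-8,775 | 6,728-9,056 | 6,875-13,138 | 6,498-13,970 |
| 3 | 6,633-9,125 | 6,476-9,433 | 7,853-19,423 | 7,485-19,675 |
| 4 | 9,300-10,774 | 9,163-10,895 | 5,771-8,478 | 5,660-8,738 |
| 5 | 9,021-11,164 | 8,837-11,316 | 7,732-13,529 | 7,390-13,800 |
| 6 | 8,715-11,393 | 8,528-11,734 | 9,252-18,413 | 8,746-19,841 |
| 7 | 13,771-16,249 | 13,577-16,562 | 9,641-5,203 (as printed) | 9,429-15,521 |
| 8 | 13,510-16,778 | 13,248-16,961 | 11,550-19,889 | 11,087-20,761 |
| 9 | 13,345-17,044 | 12,940-17,406 | 13,240-25,638 | 12,492-26,622 |

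**6. Two proofreading points.** The row 7 upper SD limit is printed below its lower limit. Simulation at 350 per arm gives 9,768-14,982. In 200 repeats of a 1,000-replicate simulation, 95% of the upper limits fell in 14,581-15,381. So 15,203 with its leading digit lost, in typing or in PDF reading, is the likely reading. For row 9, Table 2 has 25,638, while the text says "the standard deviation would fall in the range between 13,240 and 25,658".

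**The case against.** The case for treating this as a minor correction is fair in several respects.

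- **No decision hangs on it.** Table 2 describes expected precision for estimates that will inform a later study. It tests nothing and sets no threshold, so no stated target is missed at 250-300 per arm.
- **The assumed SD matters more.** The protocol says its baseline values come from a European study that may not carry over to the US, and it varies the SD. At a mean of 7,800, the width of the SD range goes from 2,557 (row 1) to 11,570 (row 3), a factor of 4.5. A widening of 7-18% is small beside that.
- **At 300 per arm the effect is near simulation noise.** The plan's 1,000-replicate widths depart from a larger simulation at 350 per arm by up to 5% (means) and 7% (SDs). In any single row, a 7-8% widening is hard to tell from that.
- **There is already an upper bound.** Sizes of 250-300 lie between 175 and 350, so a reader can infer that the average widening is below 32%.
- **The calculation itself is sound.** Table 2 reproduces at 350. The fault is an input that disagrees with other sections.

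All of this stands, and it limits the weight of the point. None of it reconciles 700 with 500-600 or supplies the precision at the planned size. The two proofreading points add no weight.

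**Conclusion.** The concern holds. Section 7.6 and Table 2 describe the precision of a trial of 700, while the rest of the plan describes one of 500-600. At 250 per arm the ranges are too narrow by about 18% of their stated width for means and 14% for SDs; at 300 per arm, by about 8% and 7%. Moderate describes the lower end of planned enrolment; at the upper end the effect is small.

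These figures assume the plan's lognormal model, equal allocation and complete cost data. Section 7.6 states no allowance for loss to follow-up, and any loss would widen the ranges further. The primary sample size is untouched: 35% against 20% at 80% power and a two-sided 5% level gives (1.96 × √0.39875 + 0.8416 × √0.3875)² / 0.15² = 137.9, so the plan's 138 per group is confirmed. The point should be fixed, but it changes neither the primary analysis nor the conduct of the trial.

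**What to change.** Reconcile Protocol 7.6 with Protocol 7.5, the Synopsis and SAP item 11. If 250-300 per arm stands:

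1. Re-run the simulation at those sizes and replace the ranges in the text and in Table 2. The 250-per-arm values above can serve as a check.
2. Replace each mention of 350 per group as the planned size, and the total of 700.
3. Restate the 175-per-group comparison against the new base. Relative to 250 per arm, the mean ranges widen about 19% (1.41 / 1.18 = 1.19) and the SD ranges about 15% (1.31 / 1.14 = 1.15).
4. Check the upper SD limits of rows 7 and 9 against the source file.

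If there is a reason to keep 350 per arm as the reference size, a sentence giving that reason and the approximate widening at 250-300 per arm would also resolve the conflict.

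The cost is a simulation that runs in under a minute and a text correction. The stated precision becomes moderately less favourable. No extra patients are needed.
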